##### **12.4.2 Exit Visit (Post Visit 6/Week 52 – Year 3)**

In addition to the assessments in Section 12.4, the following will be performed for subject's exiting the study between Visit 6/Week 52 and year 3:

- Transvaginal ultrasound to document LevoCept position
- General physical exam
- Prior to removal of LevoCept, it should be determined if the subject has had vaginal intercourse (with intravaginal ejaculation) within the last 72 hours. If confirmed, LevoCept removal and the Exit visit should be rescheduled. The subject should be instructed to avoid vaginal intercourse for 72 hours or more before LevoCept removal. If rescheduling is not possible, the subject should be instructed not to have intercourse within 72 hours of LevoCept removal due to risk of pregnancy. The subject's preferred method of contraception will be provided at the Exit visit.
  - If the subject elects a non-hormonal method of contraception, a 14-day supply will be provided by the site.
  - If the subject elects to use hormonal contraceptive pills as the preferred method of contraception, a one month supply of

hormonal contraceptive pills will be provided to the subject by the site as a contraceptive option for the first two weeks following LevoCept removal.

- The subject will also be provided with condoms to take with her as an extra precaution if the subject fails to acquire the contraception noted above.
- In addition to the above, subjects who desire to have LevoCept removed immediately and have had vaginal intercourse (with intravaginal ejaculation) within 72 hours should also be provided with emergency contraception (e.g. ella®, Plan B One-Step®)
- Subject should be reminded to avoid conception within 7 days after LevoCept removal.
- LevoCept Removal
  - LevoCept removal ease
  - LevoCept removal pain
- Urine pregnancy test will be done 17 days after removal/study exit by the subject at home, with a follow up call by the study coordinator or PI required to document results.

#### **12.4.2 Subjects Exiting the Study Due to IUD Expulsion:**

In addition to Sections 12.4 and 12.4.1, when a subject is exiting the study due to an IUD expulsion, the following will be performed:

- A urine pregnancy test will be done approximately 6-8 weeks after the exit visit by the subject at home, with a follow up call by the study coordinator or PI required to document results.

#### **12.5 Early Discontinuation Visit**

If a subject requests LevoCept removal because of an adverse event, the Study Exit Visit described in Section 12.3 above should be completed and documented on the CRF at the time of LevoCept removal. The subject will be followed until resolution of the event or 30 days after removal, whichever occurs first. Subjects experiencing an ongoing adverse event will continue to receive the appropriate follow-up medical care.

If a subject requests early discontinuation and LevoCept removal to become pregnant, the Study Exit Visit should be completed and documented on the CRF at the time of LevoCept removal. Additionally, subjects shall be followed for either; six (6) months, until they decide to no longer try to conceive or they become pregnant, whichever comes first. Outcome data regarding subject's ability to conceive, or the decision to no longer try to become pregnant will be collected via subject contact and documented.

#### **12.6 Unscheduled Visits**

Unscheduled visits must be documented on an unscheduled visit CRF. Medical evaluations will be conducted as indicated by the reason for the unscheduled visit.

### **12.7 Emergency Contraception**

If the subject suspects the LevoCept has expelled, she should contact the study site immediately. The subject should be counselled to avoid intercourse until an exam can confirm expulsion. Emergency contraception may be administered, according to product labelling, if the subject suspects expulsion has occurred and an act of intercourse might be unprotected, and she does not want the risk of pregnancy. If the subject is subsequently found to have an *in-situ* IUD and desires to continue in the study, the cycle during which she used EC will not be included in the analysis unless the subject conceives. If the IUD is expelled, she will be exited from the study and followed for 6-8 weeks for occurrence of pregnancy.

### **12.8 Lost to Follow-up**

A subject should not be considered “lost to follow-up” until the site has made at least three contact attempts (e.g. phone calls, e-mail or text message) and a certified letter is sent. The date of the certified letter or last attempted contact by the site is the subject’s exit date, whichever is later. The End of Trial and any Adverse Event or Concomitant Medication eCRFs should be submitted within a week of the subject’s lost to follow-up date. The site should continue attempts to contact the subject monthly for an additional 3 months to bring the subject back to remove the LevoCept IUD.

If after a subject is determined to be lost to follow-up and subsequently becomes available again, and the Principal Investigator determines she is a fit study subject, she can re-join the study.

## **13. Diaries**

Subjects will be instructed to complete diaries daily. Diaries are designed to collect the following information for each day of the 28-day cycle:

- Day of cycle
- Absence or presence of menstrual or other bleeding (none, spotting, normal or heavy)
- LevoCept expulsion (yes, no, suspected)
- Usage of additional birth control methods and type of birth control used
- Presence of menstrual pain or cramping
- Frequency of intercourse
- Pain with intercourse

## **14. CONCOMITANT MEDICATIONS**

Concomitant medications include any medication or health product (any prescription medications or over-the-counter preparations) taken from the time the subject signs the informed consent documents until Study Exit. Concomitant medications used as prior contraception or used to treat a prior cervical infection within 30 days of screening should also be reported. All concomitant medications, including excluded therapies, must be recorded appropriately on the eCRF.

## **15. ADVERSE EVENTS AND SERIOUS ADVERSE EVENTS**

During the study, the Investigator or study site personnel will be responsible for querying and recording adverse events (AEs) and serious adverse events (SAEs), as detailed below. For the Sponsor to fulfill safety assessment obligations, the Investigator must

report all SAEs to the Study Sponsor, whether or not they result from study participation, within 24 hours of learning of the event.

### 15.1 Definition of a Serious Adverse Event

A **serious adverse event (SAE)** is any adverse event occurring within the timelines specified in the protocol that results in any of the following outcomes:

- Death;
- Life-threatening meaning that the patient was at immediate risk of death from the event at the time that the event occurred. It does not include an event, which hypothetically might have caused death if it occurred in a more severe form.
- Inpatient hospitalization or prolongation of existing hospitalization;
- Persistent or significant disability/incapacity;
- Congenital anomaly/birth defect in the offspring of a subject who received study device; or
- Important medical events that may not result in death, be immediately life-threatening, or require hospitalization, may be considered an SAE when, based upon appropriate medical judgment, they may jeopardize the subject and may require medical or surgical intervention to prevent one of the outcomes listed in this definition. Examples of serious adverse events include, but are not limited to: intensive treatment in an emergency room, hospitalization for any reason, and extensive treatment at home for an adverse event. An ectopic pregnancy is considered a serious adverse event.

### 15.2 Definition of An Adverse Event

An **adverse event** is any untoward medical occurrence in a clinical investigation subject administered an investigational product and which does not necessarily have to have a causal relationship with this treatment. An AE can, therefore, be any unfavorable and unintended sign (that could include a clinically significant abnormal laboratory finding), symptom, or disease temporally associated with the use of a medicinal product, whether or not considered related to the medicinal product.

- Any medical condition or clinically significant laboratory abnormality with an onset date before the first date of attempted study device placement is usually considered to be pre-existing, and should not be documented in the eCRF as an AE, unless there is an increase in frequency or intensity of that AE, but should be recorded as medical history.
- Any AE (i.e., a new event or an exacerbation of a pre-existing condition) with an onset from the first attempt of study device placement through Study Exit should be recorded as an AE on the eCRF. All AEs must be recorded on the AE eCRF regardless of the severity or relationship to study device. It is important that Investigators also report all AEs that result in expulsion or removal of the investigational product being studied, whether serious or non-serious.

Pregnancy is an outcome, and not an adverse event in this study.

### 15.3 Causality: Serious Adverse Event and Adverse Event Relationship to Study Treatment

The Investigator will assess the relationship of the SAE and AE to study device placement procedure (procedure) or study device by using the following general guidelines:

**Not Related:** A causal relationship between the study device and the AE can be ruled out (e.g., based on the temporal sequence, absence of a reasonable pathophysiological mechanism, or direct evidence of actual cause).

**Unlikely related:** A clinical event, including laboratory test abnormality, with a temporal relationship to procedure or study device initiation which makes a causal relationship improbable, and in which other drugs, chemicals or underlying disease provide plausible explanations.

**Probably Related:** A clinical event, including laboratory test abnormality, with a reasonable time sequence to first attempt of study device placement, unlikely to be explained by concurrent disease or other drugs or chemicals. Information on drug withdrawal may be lacking or unclear.

**Related:** A clinical event, including laboratory test abnormality, with a reasonable time sequence to first attempt of study device placement, cannot be attributed to concurrent disease or other medical devices, drugs, or chemicals, and which follows a clinically reasonable response on withdrawal.

#### 15.3.1 Clarification of Adverse Events Related to Study Procedures

Any untoward event that occurs from the beginning of the study device placement procedure until completion of placement, or from the beginning of the removal procedure until the completion of removal, will be reported as an AE. The AE should be recorded on the AE eCRF with a causality assessment of “related to study device placement procedure.” If the AE also meets the criteria for an SAE, an SAE eCRF should be completed and submitted to Sponsor.

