### **Safety and Other Outcome Measures**

LevoCept ease of placement, placement success, expulsions, and removal success will be descriptively summarized.

Safety evaluations will be based on the incidence of adverse events and serious adverse events and by relationship to the study device or study device placement procedure.

Study device tolerability will be based on changes in bleeding and spotting patterns and study discontinuation (including reasons for discontinuation).

Safety analyses will be based on the experience of all subjects who had attempted study device placement and provided any relevant data. Tolerability analyses will be based on the experience of all subjects who received a study device and provided any relevant data.

Subjects will record frequency and intensity of vaginal bleeding through a daily e-diary. The number of bleeding or spotting days will be summarized for each cycle. In addition, bleeding and spotting will each be summarized separately. Bleeding analyses will include all subjects who had a study device placed and have at least 1 cycle where they were not pregnant and were providing bleeding-related e-diary data on the days in the reference period.

In general, summaries of quantitative variables will include the sample size, mean, median, standard deviation, minimum, and maximum. For qualitative (categorical) variables the summaries will include the number and percentage of subjects in each category.

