### **5. OBJECTIVES**

The scientific objective of this study is to evaluate the effectiveness, study device placement, safety, and tolerability of the LevoCept Intrauterine Contraceptive as birth control in parous and nulliparous women of child-bearing age.

The purpose of the study is to obtain the safety and effectiveness data necessary to support initiation of a longer-term Phase III Pivotal Clinical Study for LevoCept.

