### **Adverse Events**

The number and percentage of subjects with each adverse event and serious adverse event will be presented in a table by MedDRA system-organ class and preferred term. Summaries will also be presented by relationship to the LevoCept placement or removal procedure and the severity of the adverse event. All adverse events will be summarized with special attention to those events that may be related to an intrauterine contraceptive, including:

- Acne
- Amenorrhea
- Back pain
- Breast cancer
- Breast tenderness
- Depression/depressive mood
- Dysmenorrhea
- Dyspareunia
- Ectopic pregnancy
- Embedment
- Expulsion, partial or complete
- Headache, migraine
- Intrauterine pregnancy
- Irregular menstrual bleeding
- Leukorrhea
- Ovarian cysts
- Pain and cramping
- Pelvic infection
- Perforation
- Sepsis
- Vaginitis
- Vasovagal reaction immediately after placement

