4.2 Safety and other Variables

Safety and other measures are study device placement, safety, and tolerability.

1. Placement success

Device successfully deployed at first try rate is defined as the percentage of the number of subjects with successful deployment at first attempt among the total number of subjects with first attempt.

Device successfully deployed at second try rate is defined as the percentage of the number of subjects with successful deployment at second attempt among the total number of subjects with second attempt.

Device successfully deployed rate is defined as the percentage of the number of subjects with successful deployment in either first or second attempt among the total number of subjects enrolled.

2. Ease of placement

Five categories of how easy the device placement have been collected: Very easy, Easy, Neither Easy nor Hard, Hard and Very Hard.

Five categories of device placement pain as rated by the subject: No Pain, Some Pain, Painful, Moderately Painful and Very Painful.

Question of insertions requiring mechanical cervical dilatation has been collected.

3. Adverse events

All Adverse Events (AEs) will be coded from verbatim text to PTs and grouped by system organ class (SOC) using the Medical Dictionary for Regulatory Activities (MedDRA) (version 17.0). AEs will be collected from the beginning of the study device placement procedure through to study exit. Pre-existing conditions that worsen during a study are to be reported as AEs.

Throughout the study, all AEs will be evaluated by the investigator and noted in the AE section of the CRF.

AEs will be classified as not related, unlikely related, probably related, or related events when considering their relationship to study device, study device placement/removal procedure. Also, AEs will be classified as mild, moderate, severe when considering their severity. If the severity or relationship of an AE is missing, the severity/relationship will be coded as severe, related, respectively, i.e. worst case scenario.

Treatment-emergent AEs (TEAEs): AEs that develop or that worsen in intensity during or after the exposure to the study device.

See Appendix 1 for handling of partial dates for AEs. If it cannot be determined whether the AE is treatment emergent due to a partial onset date then it will be counted as such.

Other AE variables include study device related AEs, AEs leading to study withdrawal, AEs leading to deaths, life threatening AEs, and serious AEs (SAEs).

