6.2.9.1 Adverse Events

Number of AEs will be summarised by SOC and/or PT for the following categories of TEAEs: all AEs, SAEs, AEs related to study device, AEs related to study device placement/removal procedure, AEs leading to death, AEs leading to study device removal and AEs as primary reason for exiting study. Patients with more than one occurrence of the same SOC (PT) will be counted only once within the SOC (PT) categorisation.

AEs will also be summarised similarly by severity (i.e. mild, moderate, severe), relationship to study device (i.e. not related, unlikely related, probably related, related), relationship to placement/removal procedure (i.e. not related, unlikely related, probably related, related) and onset time frame (i.e. 0-3 months, >3-6 months, >6-12 months, >12 months). Should a subject experience more than one occurrence of the same SOC (PT), the subject's worst occurrence (worst intensity/most related causality) will be retained in the tabulation.

All AEs, including AEs that started prior to the study device placement, will be presented in data listings. In addition, separate listings of all SAEs, AEs related to study device, AEs related to study device placement/removal procedure, AEs leading to death, AEs leading to study device removal and AEs as primary reason for exiting study will be provided. In case of any AEs reported from study device insertion failure subjects, selected AE tables will be repeated for all enrolled subjects for all AEs.

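### Protocol 15.3.1 labels removal events as placement-related, and the SAP's combined placement/removal category gives an AE rate for neither procedure

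*Protocol*

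**What the plan says.** Protocol 15.3.1 covers two periods, the placement procedure and the removal procedure. Any untoward event in the second, "from the beginning of the removal procedure until the completion of removal, will be reported as an AE". The next sentence applies to both periods: "The AE should be recorded on the AE eCRF with a causality assessment of", completed by a label that names the placement procedure and not removal.

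Other sections do not agree on which procedure is meant:

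- Protocol 15.3 has the investigator rate the "relationship of the SAE and AE to study device placement procedure (procedure) or study device". Removal is not named, and the two upper grades are defined by timing relative to the first placement attempt.
- The protocol synopsis (Statistical Methods, Safety and Other Outcome Measures) reports safety "by relationship to the study device or study device placement procedure".
- Protocol 20.7 (Adverse Events) plans summaries "by relationship to the LevoCept placement or removal procedure and the severity of the adverse event".
- SAP 4.2 classifies AEs by "relationship to study device, study device placement/removal procedure", and SAP 6.2.9.1 tabulates them by "relationship to placement/removal procedure (i.e. not related, unlikely related, probably related, related").

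Tables 14.3.1.1.1, 14.3.1.2.1 and 14.3.1.10 and Listings 16.2.7.1 and 16.2.7.3 carry this one combined category. Table 14.3.1.10 takes the layout of Table 14.3.1.9: percentages over the Safety population, each woman counted once per level at her closest relationship. SAP 5.3 limits the Safety population to women whose device was successfully placed.

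**The concern.** A site that follows 15.3.1 would record an event at a year-three removal as related to placement, although placement finished long before. A second attempt must fall within a week of the first (Protocol 12.2), and devices are not replaced after expulsion or removal (Protocol 4.5). The analysis does not undo this, because it never separates the two procedures.

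The study sets out to "evaluate the effectiveness, study device placement, safety, and tolerability of the LevoCept Intrauterine Contraceptive", and its data are meant to support a Phase III trial. Placement and removal are different procedures, up to three years apart, and the women who undergo them are not the same set. SAP 7 plans the same analyses at one year and at the end. A reader of either report could not tell how many procedure-related AEs arose at insertion, and a change between the reports could come from removals alone.

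**Working it through.** **1. Does any planned output give a procedure-specific AE rate?**

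| Output | Procedure attribution | Denominator |
|---|---|---|
| 14.3.1.1.1 | combined | Safety population |
| 14.3.1.2.1 | combined | number of events |
| 14.3.1.10 | combined | Safety population |
| 14.3.1.1.2, 14.3.1.2.2 | combined | as the two overall tables above, for All Enrolled |
| 14.3.1.12, 14.3.1.13 | none (AEs by onset period, not crossed with procedure) | Safety population |
| 14.3.5.2, 14.3.5.3 | separate, but ease, pain and difficulty rather than AEs | All Enrolled; Safety |

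None does. In Table 14.3.1.10 the denominator fits neither procedure. It leaves out women who had a placement attempt that failed, and it includes women who have had no removal. The All Enrolled tables restore the failed attempts but keep the combined category, and no All Enrolled version of 14.3.1.10 is indexed.

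**2. How far could the combined figure move?** The documents state no AE rate for either procedure, so there is no figure to reproduce. For illustration only, let *p* be the share of women with an AE at placement, *q* the AE rate per removal and *r* the share of women with a removal. All three are assumed, and placement and removal events are taken as independent. Because each woman counts once,

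combined rate = *p* + (1 − *p*) × *q* × *r*.

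With *p* = 5%, a placement-only rate stays at 5.0% throughout. The combined rate is:

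| *q* | *r* = 20% | *r* = 50% | *r* = 90% |
|---|---|---|---|
| 0% | 5.0% | 5.0% | 5.0% |
| 1% | 5.2% | 5.5% | 5.9% |
| 5% | 6.0% | 7.4% | 9.3% |
| 10% | 6.9% | 9.8% | 13.6% |

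For example, 5% + 0.95 × 5% × 0.90 = 9.3%. Among 250 women the extra count at *r* = 90% is 250 × 0.95 × 0.05 × 0.90 = 10.7 for *q* = 5%, and 250 × 0.95 × 0.01 × 0.90 = 2.1 for *q* = 1%. Over *p* = 2–10%, *q* = 1–10% and *r* = 20–90%, the excess (1 − *p*) × *q* × *r* runs from 0.90 × 1% × 0.20 = 0.2 to 0.98 × 10% × 0.90 = 8.8 percentage points.

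**3. The denominator can pull the other way.** Suppose 5% of placements fail and 20% of those women have an AE (both assumed). The placement rate over all women with an attempt is then 0.95 × 5% + 0.05 × 20% = 5.75%, against 5.0% in the Safety population. The net direction in Table 14.3.1.10 is therefore not settled.

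**4. Can the events be separated?** Largely, yes. AE start dates are in Listing 16.2.7.1, placement-attempt dates in Listing 16.2.5.1 and removal dates in Listing 16.2.5.2.

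**The case against.** The strongest reply is that the SAP plans no placement-only AE rate, so there is none to inflate. Its category is openly labelled placement/removal, matches Protocol 20.7, and is non-specific rather than biased. The AE listing shows a single placement/removal relationship field with no placement-only option, so the phrase in 15.3.1 may be a wording slip, and it says should rather than must. Placement as an outcome means success and ease (Protocol 5.2, SAP 4.2), and ease and pain are tabulated separately for placement and for removal. Cumulative AE tables normally grow with follow-up, and the dates allow a split at any time.

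Most of this stands, and it limits the point. A reader might infer that the trial will publish an inflated placement AE rate that climbs with every removal. The documents do not support that. No planned table claims to show such a rate. The subject percentage rises only when a removal brings a procedure-related AE in a woman not already counted.

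The reply leaves three things unanswered. The protocol contradicts itself on which procedure is being rated. The split is possible but nobody has planned it. The denominator of Table 14.3.1.10 suits neither procedure.

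**Conclusion.** The point holds as a conflict between sections and a gap in the planned output. Protocol 15.3.1, 15.3 and the synopsis must be reconciled with Protocol 20.7 and the SAP, and no planned table reports AEs of either procedure over the women who underwent it. An overstated placement rate would arise only if someone used the 15.3.1 label, or the synopsis wording, to report placement AEs alone.

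The size cannot be derived from the documents. It depends on the AE rate at removal, the share of devices removed and the overlap with women already counted, and it is nil if removals cause no AEs. The tabulated figures show how the combined rate behaves under assumed inputs; they are not estimates for this trial. It would also go too far to say that the trial cannot report these rates, since the necessary dates are collected.

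**What to change.** **Protocol.** In 15.3.1, label events during removal as related to the removal procedure and keep the placement label for events during placement attempts. Bring 15.3 and the synopsis into line with 20.7.

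**SAP.** For procedure-related AEs, derive a placement/removal flag by comparing the AE start date with the attempt and removal dates. State in advance how an event that starts after the procedure day is assigned, because the date match alone does not settle it. Split the procedure rows of Tables 14.3.1.1.1, 14.3.1.2.1 and 14.3.1.10, and show the flag in Listing 16.2.7.3. For subject percentages, use all women with a placement attempt for placement and women with a removal for removal. Table 14.3.1.2.1 is based on events, so there the split applies to event counts. Since SAP 1.2 dates Day 1 from successful deployment, the placement rows should also take in AEs from earlier failed attempts.

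**Cost.** A corrected sentence and two aligned sections in the protocol, one derived flag, a few extra table rows, and some judgement on events that begin after the procedure. No new data are needed.
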